4.2.3 Secondary Hypotheses

For continuous variables and ordered categorical variables the Wilcoxon signed rank test will be applied and for binary variables the Binomial test will be applied when testing the null-hypothesis that the Baha 6 Max SP and the Baha 5 SP are equal.

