6 OBJECTIVES AND ENDPOINTS

Primary Objectives	Primary Endpoints

To compare hearing performance of speech in noise between Baha 6 Max SP and the unaided hearing (superiority).
 
To compare the preference of device between Baha 6 Max SP and Baha 5 SP
	
Adaptive speech in noise [signal-to-noise ratio, 50% speech understanding]
 
Preference of device

Secondary Objectives	Secondary Endpoints

To compare hearing performance between Baha 6 Max SP and Baha 5 SP in a home/normal environment hearing environment
	
 • Diary 
 ◦ Daily use of the SP (hours) ◦ Change of battery ◦ Switch to their own SP and reason for change

To compare hearing performance between Baha 6 Max SP and Baha 5 SP.
	
 • Adaptive speech in noise [signal-to-noise ratio, 50% speech understanding] • Thresholds audiology, sound-field [0.25, 0.5, 1.0, 2.0, 3.0, 4.0, 6.0, 8.0, 9.0 and 10.0 kHz] • Speech in quiet [% correctly perceived words at 65dB SPL] • Evaluation of sound quality and listening effort through sound clips

To compare hearing performance between Baha 6 Max SP and unaided.
	
 • Thresholds audiology, sound-field [0.25, 0.5, 1.0, 2.0, 3.0, 4.0, 6.0 and 8.0 kHz] • Speech in quiet [% correctly perceived words at 65dB SPL]
Safety Objective	Safety Outcome measures
Adverse events (AEs)	Information will be collected from Visit 1 and onwards.
Device deficiency (DDs)	Information will be collected from Visit 1 and onwards.

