9 STATISTICAL CONSIDERATIONS

9.1 General Statistical Considerations

The investigation will have two primary analyses, one regarding Adaptive speech in noise between Baha 6 Max SP and unaided hearing ($\alpha = 0.005$) and one regarding preference between Baha 6 Max SP and Baha 5 SP ($\alpha = 0.045$). These endpoints will be evaluated using the decision rules of the Holm's test. (Ref NEJM2). With these procedures we will have a total type I error <0.05 .

For the comparison between the Baha 6 Max SP and unaided the design don't take care of period effect so the statistical analyses will be paired. For the comparison between Baha 6 Max SP and Baha 5 SP a cross over design was applied and the statistical analyses will be adjusted for period effect.

The main results for all outcome variables are the estimate of mean differences with 95% confidence interval (CI) with a descriptive p-value. The p-value will only have a confirmatory value for the two primary analyses.

For comparison between the Baha 6 Max SP and unaided Fisher's non-parametric permutation test for paired observations will be used for continuous variables and Sign test for dichotomous variables and ordered categorical variables.

For the comparison between Baha 6 Max SP and Baha 5 SP the following period adjusted analysis should be performed for continuous variables: For each subject take the difference between the measurement in second period and the measurement in first period. Then analyse these differences between the subjects randomised to Baha 6 Max SP in the first period and the subjects randomised to Baha 5 SP in the first period with Fisher's two-sided non-parametric permutation test. The Fisher's permutation test is preferable because it is non-parametric and gives consistent 95% CI.

For the comparison between Baha 6 Max SP and Baha 5 SP the following period adjusted analysis should be performed for dichotomous and ordered categorical variables: For each subject take the difference as, improved no change and worsened, between the measurement in second period and the measurement in first period. Then analyse these ordered categorical differences between the subjects randomised to Baha 6 Max SP in the first period and the subjects randomised to Baha 5 SP in the first period with Mantel-Haenszel chi-square test.

For comparison of preference of device between Baha 6 Max SP and Baha 5 SP the Sign test will be used.

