9.7 Secondary Endpoint Analyses

All the secondary endpoints in section 8.2.2 will be analysed according to the statistical methods given in section 8.1 General Statistical Considerations on both the FAS population and the Per Protocol population. The two primary efficacy analyses will also be performed on the Per Protocol population

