1 INTRODUCTION

This document is a companion document to the Clinical Investigation Plan (CIP). It includes a comprehensive description of the intended statistical analyses to be performed and the presentation of the results and data collected for the study.

This Statistical Analysis Plan (SAP) is based upon final CIP version 3.0

Any deviation from the Statistical Analysis Plan will be reported in the Clinical Investigation Report (CIR).

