3.2 Endpoints to be used for the secondary objectives

- Daily use of sound processors (hours) from Diary, Only Baha 6 Max SP vs Baha 5 SP
- Change of battery from Diary, Only Baha 6 Max SP vs Baha 5 SP
- Switch to their own sound processor and the reason for change from Diary (Only Baha 6 Max SP vs Baha 5 SP)
- Adaptive speech in noise [signal-to-noise ratio, 50% speech understanding] Baha 6 Max SP and Baha 5 SP
- Thresholds audiology, sound-field [0.25, 0.5, 1.0, 2.0, 3.0, 4.0, 6.0, 8.0 9.0 and 10.0 kHz]
- Speech in quiet [% correctly perceived words at 65dB SPL]
- Evaluation of sound quality and listening effort through sound clips. Only Baha 6 Max SP and Baha 5 SP.

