4.3 Analysis Datasets

4.3.1 Intent-to-Treat

The Full Analysis Set will consist of all correctly included and randomized subjects that have at least one measurement on two of the periods Baha 6 Max SP Baha 5 SP.

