4.4.4 Additional Statistical Analyses

No additional analysis will be conducted.

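### The SAP omits the protocol's secondary comparison of Baha 6 Max with unaided hearing on sound-field thresholds and speech in quiet

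*SAP*

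**What the plan says.** **Protocol.** Section 6 lists three secondary objectives. The third is "To compare hearing performance between Baha 6 Max SP and unaided", with sound-field thresholds and speech in quiet as its endpoints. Sections 7.3.4 and 7.3.5 schedule both tests unaided at Visit 3. Section 9.1 gives the method: "For comparison between the Baha 6 Max SP and unaided Fisher's non-parametric permutation test for paired observations will be used for continuous variables". It also says that the main result for every outcome variable is a mean difference with a 95% confidence interval, and that p-values are confirmatory only for the two primary analyses. Section 9.7 carries those methods to the secondary endpoints, on both the full analysis set and the per protocol population: "All the secondary endpoints in section 8.2.2 will be analysed according to the statistical methods given in section 8.1 General Statistical Considerations". The section numbers in that sentence are wrong, but the heading it names is that of 9.1.

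**SAP.** Section 1 describes the document as a companion to the protocol and says of it: "It includes a comprehensive description of the intended statistical analyses to be performed". Section 3.2 lists thresholds and speech in quiet among the secondary endpoints. Section 4.2.3 prescribes the Wilcoxon signed rank test or the Binomial test, and names one comparison: "when testing the null-hypothesis that the Baha 6 Max SP and the Baha 5 SP are equal". Section 4.4.4 states: "No additional analysis will be conducted". Section 4.3.1 defines the full analysis set by "at least one measurement on two of the periods Baha 6 Max SP Baha 5 SP".

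**The concern.** A SAP should turn each protocol objective into an analysis. Here one stated objective has a method in the protocol and none in the SAP. SAP 4.4.4 then appears to close the list. SAP section 1 also requires deviations from the SAP to be reported, so on a literal reading, running the protocol's own analysis would count as a deviation.

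The objective is not marginal. Protocol 7.1.1 gives testing against unaided hearing, for regulatory approval, as a main purpose of the study. Protocol 4.2.2 supports the performance of Baha 5 with three kinds of evidence against the unaided condition: sound-field thresholds, speech in quiet and speech in noise. Two of those three are the endpoints left without a SAP analysis. They describe audibility by frequency and benefit in quiet, which the speech-in-noise primary does not cover.

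**Working it through.** The plan gives no figure for this comparison. Its sample sizes (15 and 16) belong to the two primary analyses and do not enter here. The check is a side-by-side reading and a count.

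**1. Is there any SAP analysis against unaided hearing for these endpoints?**

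| Item | Protocol | SAP |
|---|---|---|
| Objective or endpoint | Section 6: Baha 6 Max vs unaided, thresholds and speech in quiet | 3.2: both endpoints listed, comparator not stated |
| Secondary test | 9.1 and 9.7: paired Fisher permutation test vs unaided for continuous variables | 4.2.3: Baha 6 Max vs Baha 5 only |
| Full analysis set | 9.5.1: data in two of the three periods, unaided included | 4.3.1: names only the Baha 6 Max and Baha 5 periods |
| Per protocol set | 9.5.2: all three periods | 4.3.2: all three periods |
| Other analyses | none stated | 4.4.4: none |

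The SAP names unaided hearing as a comparator only in 4.1, in the sample-size text for speech in noise. For thresholds and speech in quiet the answer is no.

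**2. Does the omission look deliberate?** The SAP gives no reason for it, and two of its own sections point the other way. Section 3.2 limits the diary and sound-clip items to the two processors but puts no such limit on thresholds or on "Speech in quiet [% correctly perceived words at 65dB SPL". Section 4.3.2 still requires measurements in all three periods. The SAP thus expects unaided data for which it plans no test.

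**3. Does the version gap explain it?** The SAP is based on protocol version 3.0. The protocol's change history lists only section 8.4 as changed in version 4.0. Sections 6 and 9 are not listed, so the gap does not explain the conflict.

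**4. Would correcting the primary analysis cure it?** SAP 4.2.2 also replaces unaided hearing with Baha 5 for the first primary. Restoring that comparison repairs speech in noise only. SAP 4.2.3 would still leave thresholds and speech in quiet without an unaided comparison.

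**5. Size.**
- Objectives affected: 1 of 3 secondary objectives.
- With the unaided row of protocol section 6 (0.25 to 8 kHz): 8 frequencies + 1 word score = 9 comparisons.
- With the list in the synopsis, protocol 7.3.4 and 9.2, and SAP 3.2 (0.25 to 10 kHz): 10 frequencies + 1 word score = 11 comparisons.
- Each has up to 16 paired differences, if all 16 planned subjects complete Visit 3.

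**6. Analysis set.** Read literally, SAP 4.3.1 needs both processor periods. A subject with Baha 6 Max and unaided data but no Baha 5 data is in the full analysis set under protocol 9.5.1 and outside it under SAP 4.3.1, although that subject supplies a valid paired difference. With no dropouts expected the number should be small, but an added test would lack a matching analysis set.

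**The case against.** The strongest reply is that nothing is lost, because the protocol already specifies the analysis and the SAP is only its companion. The SAP does not say that it replaces protocol section 9. SAP 4.4.4 can be read as excluding only analyses beyond those planned, and the protocol comparison is planned. SAP 3.2 and 4.3.2 keep the unaided data in view, and SAP 4.7 lists all subject data. On this view, 4.2.3 is an incomplete sentence.

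Much of this stands. A reader might infer that the objective has no analysis anywhere, or that the sponsor chose to drop it. The documents support neither: protocol 9.1 and 9.7 give a method, and the SAP announces no departure from it. Nor is it certain that the unaided data would go unanalysed, since that depends on how 4.4.4 is read and which document the analyst follows. Unaided data in every subject is likewise the plan and not a certainty, because protocol 9.1 provides for subjects who finish the crossover but miss the final visit.

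Two further points are fair. The count of 9 or 11 shows extent; it does not show bias, loss of power or inflated error. And the cause is probably shared with the changed comparator in SAP 4.2.1 and 4.2.2, so all of these can be corrected together.

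The reply does not remove the conflict. The SAP claims comprehensive coverage, names different tests and a single comparator for the secondaries, and leaves the unaided period out of its full analysis set. Someone working from it would not produce the protocol's comparison.

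**Conclusion.** The point holds as an omission and a contradiction: the SAP leaves out a comparison that protocol sections 6, 9.1 and 9.7 require, and its full analysis set departs from protocol 9.5.1. One of three secondary objectives, covering 9 or 11 comparisons, has no planned result in the SAP.

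The consequence is moderate. These results are descriptive under protocol 9.1, so the confirmatory conclusions do not depend on them. What would be missing is the set of mean differences and 95% confidence intervals that the protocol promises.

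This rests on two assumptions: that thresholds and percentage word scores count as continuous variables under protocol 9.1, and that SAP 4.2.3 and 4.4.4 are applied as written.

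**What to change.** 1. **SAP 4.2.3.** Add that, for sound-field thresholds and speech in quiet, the within-subject difference Baha 6 Max minus unaided is analysed with Fisher's paired permutation test. Report the mean difference, its 95% confidence interval and a descriptive p-value, on the full analysis set and the per protocol set.
2. **SAP 4.3.1.** Restore the unaided period in the full analysis set definition, to match protocol 9.5.1.
3. **If the objective was meant to be dropped,** say so in the SAP and justify the departure from the protocol.
4. **Separately, the frequency list.** Reconcile the unaided row of protocol section 6, which stops at 8 kHz, with the synopsis, protocol 7.3.4 and 9.2, and SAP 3.2, which run to 10 kHz.

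Items 1 and 2 take a few SAP sentences and need no measurement beyond those the protocol already schedules. Item 4 is a small protocol edit, and under protocol section 18 an amendment requires notification to the ethics committee, so the total cost is slightly more than a SAP revision.

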4.3 Analysis Datasets

4.3.1 Intent-to-Treat

The Full Analysis Set will consist of all correctly included and randomized subjects that have at least one measurement on two of the periods Baha 6 Max SP Baha 5 SP.

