7.2.1 Inclusion Criteria

Subjects must meet all the inclusion criteria described below to be eligible for this clinical investigation.

1. Adult subject (18-<70 years of age)
2. At least 12 months experience from using a Baha Connect system (percutaneous Baha)
3. Subject with a conductive or mild to moderate mixed hearing loss. that would benefit from improved hearing from bone conduction devise as judged by the research audiologist
4. Willing and able to provide written informed consent

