7.2.5 Enrolment & Study Duration

The following subject status definitions apply:

Screened: A consented subject who is being assessed for eligibility according to the Screening requirements.

Screen Fail: A consented subject that has been determined to not meet all eligibility criteria for enrolment.

Enrolled: First use of the IMD or comparator following completion of screening activities and confirmation of eligibility

The expected duration of each subject's participation in the clinical investigation is 3 weeks, from the time of informed consent to the End of Study visit.

The enrolment period for the clinical investigation is anticipated to be 6 weeks from the time of first subject consent to enrolment of the last subject.

The anticipated total duration of the clinical investigation is therefore 8-9 weeks.

Clinical Investigation completion is last subject last visit. In the event of an ongoing SAEs/SADEs at the time of this last visit, the clinical investigation completion will be extended for a further 30 days, or until resolution or stabilisation of the event, whichever comes first.

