9.5 Analysis Populations

9.5.1 Full Analysis Set

The Full Analysis Set will consist of randomized subjects that have at least one measurement on two of the periods Baha 6 Max SP, Baha 5 SP and unaided.

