9.5.2 Per Protocol Population

The Per protocol population will consist of all randomized patients that have measurements on all primary and secondary variables on all three periods and have no major protocol violations.

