4.3.2 Per Protocol Dataset

The Per Protocol Analysis Set (PPAS) will consist of all subjects included in the FAS who have measurements on all primary and secondary variables on all three periods and have no major protocol violations.

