4.7 Presentation of Data

Listing of all subject data will be done and presented in the statistical report.

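### The SAP's full analysis set adds an undefined eligibility filter that the protocol lacks and leaves an excluded subject in neither efficacy set; the per-protocol completeness rule cannot be met as written

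*SAP*

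**What the plan says.** **Full analysis set.** Protocol 9.5.1 takes "randomized subjects that have at least one measurement on two of the periods Baha 6 Max SP, Baha 5 SP and unaided". SAP 4.3.1 takes "all correctly included and randomized subjects that have at least one measurement on two of the periods Baha 6 Max SP Baha 5 SP". The SAP version adds a condition on inclusion and drops the unaided period. The SAP's own definitions table is empty. Protocol 9.1 puts the main analyses on the FAS, and per protocol is complementary.

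**Per-protocol set.** Protocol 9.5.2 starts from "all randomized patients that have measurements on all primary and secondary variables on all three periods and have no major protocol violations". SAP 4.3.2 starts from "all subjects included in the FAS who have measurements on all primary and secondary variables on all three periods", again without major violations. Protocol 9.7 requires both primary analyses to be repeated on this set.

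**What else is planned.** SAP 4.4.4 states: "No additional analysis will be conducted". SAP 4.7 adds only: "Listing of all subject data will be done and presented in the statistical report".

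**Eligibility.** Protocol 7.2.5 defines enrolment as "First use of the IMD or comparator following completion of screening activities and confirmation of eligibility". Inclusion criterion 3 (Protocol 7.2.1) turns partly on expected benefit from a "bone conduction devise as judged by the research audiologist".

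**The concern.** The FAS carries both confirmatory analyses, and the two documents give different rules for who is in it. Eligibility should already be settled before a device is first used. The added words therefore either do nothing or allow eligibility to be judged again after randomisation. If the second is meant, no criteria are named, no timing relative to the results is fixed, and no planned analysis keeps the subject. The home test is open label, preference is recorded at Visit 3, and part of one entry criterion is a judgement by the research audiologist. An exclusion could therefore be made with the preference known.

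The protocol already deals with breaches in the per-protocol set, through its condition on major violations. The SAP wording moves that decision into the main analysis.

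The per-protocol rule has a different fault. Taken literally, nobody qualifies. Taken loosely, it selects on completeness of unrelated secondary data rather than on adherence that bears on the comparison.

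**Working it through.** **1. The plan's own sample sizes.** Inputs are from Protocol 9.4; SAP 4.1 repeats the first.

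- Speech in noise: mean difference 16 dB, SD 12.5, two-sided alpha 0.005. Effect size is 16/12.5 = 1.28. Paired-t power (noncentrality 1.28√n, n − 1 df) is 89.2% at n = 14, 92.4% at n = 15 and 94.7% at n = 16. The stated 15 for 90% power is reproduced. Simulating the exact paired permutation test gave 91.3% at n = 15.
- Preference: 86%, two-sided sign test at 0.045. At n = 16, 13 preferences are needed (exact two-sided level 0.0213) and power is 82.4%. At n = 15, 12 are needed (0.0352) and power is 85.2%. The stated 16 does give at least 80%.

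**2. Set membership.** Take a randomised subject with full data who is later ruled not correctly included.

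| | FAS | Per protocol |
|---|---|---|
| Protocol | in | in, completeness rule aside, unless the breach is a major violation |
| SAP | out | out, because the set is nested in the FAS |

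With SAP 4.4.4 planning nothing more, the subject's efficacy data appear only in the listing. The SAP follows CIP version 3.0, but the change history shows only section 8.4 altered in version 4.0, so the version gap does not explain the difference.

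**3. Effect of one exclusion on the preference test.** The exact two-sided sign test was run for every count at n = 16, assuming all 16 subjects state a preference. The conclusions are the same at 0.045 and 0.05.

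| 16 subjects | p | After one exclusion | p |
|---|---|---|---|
| 11/16 | 0.2101 | 11/15 (a Baha 5 preferrer removed) | 0.1185 |
| 12/16 | 0.0768 | 12/15 (a Baha 5 preferrer removed) | 0.0352 |
| 13/16 | 0.0213 | 12/15 (a Baha 6 Max preferrer removed) | 0.0352 |

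Only the middle row changes the conclusion. Its mirror, 4/16 to 3/15, favours Baha 5. No single exclusion removes a significant result.

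- At 86%: P(12 of 16) = 1820 × 0.86^12 × 0.14^4 = 0.1144. Four of the 16 then prefer Baha 5, so an exclusion unrelated to preference changes the conclusion with probability 0.1144 × 4/16 = 0.0286.
- With no true preference, the chance of a result favouring Baha 6 Max is 697/65,536 = 1.06% with 16 subjects. It is 576/32,768 = 1.76% with 15 after an unrelated exclusion. In the worst case, where every 12/16 becomes 12/15, it is 2,517/65,536 = 3.84%. The benchmark is 0.045/2 = 2.25%.

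**4. Effect on the first primary.** Losing one subject lowers paired-t power from 94.7% to 92.4%. This applies to the protocol's comparison with unaided hearing. SAP 4.2.2 states a different primary comparison, which is a separate conflict.

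**5. Dropping the unaided period.** On the wording, a subject with Baha 6 Max and unaided data but no Baha 5 data leaves the FAS. The schedule, however, places the sound-clip rating of both devices at Visit 3, the same visit as the unaided tests. A subject who completes that visit has a Baha 5 measurement anyway, so the practical effect is close to nil.

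**6. The per-protocol rule.** Protocol 9.2 lists eight variables: speech in noise, preference, daily use, battery change, switch to own processor, thresholds, speech in quiet and sound clips. Preference, the three diary items and sound clips (5 of 8) are limited to the two devices. Requiring all eight in all three periods leaves 0 of 16 subjects.

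**The case against.** *Correctly included* can be read simply as having met the documented entry criteria. Protocol 7.3.1 requires audiograms that show the type of hearing loss, so criterion 3 is not judgement alone. Protocol 13 requires every deviation to be recorded for reporting in the Clinical Investigation Report, so an exclusion would not be hidden. An ineligible subject might fail the condition on major violations in any case. The missing unaided period looks like dropped text. The per-protocol rule is naturally read as each variable where it is scheduled. The figures are small, and the 3.84% needs selective removal that nothing in the documents suggests.

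Most of this stands as a limit on severity. It does not remove the point: none of it puts an excluded subject back into an SAP efficacy set or supplies criteria or timing for the exclusion. The loose per-protocol reading still lets one missing diary item remove a subject from the per-protocol versions of both primary analyses. It is also fair to say that major protocol violations are not defined in either document, so a fix that relies on that term should define it.

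**Conclusion.** The concern holds and should be corrected, although its likely effect on the results is small. The two FAS definitions conflict, and the SAP leaves a subject excluded on eligibility without a planned efficacy analysis. The numerical exposure is one configuration, 12 of 16 with a Baha 5 preferrer removed. It arises 2.9% of the time at 86% preference if exclusion is unrelated to preference. With no true preference, such an unrelated exclusion keeps the favourable error at 1.76%, under 2.25%; only systematic selective exclusion takes it to 3.84%. These figures illustrate exposure and do not predict an effect. They assume one exclusion and 16 stated preferences. The omission of the unaided period is a contradiction with practically no effect. The per-protocol rule is unmeetable as written, but it touches only the complementary analyses and not the main FAS results.

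**What to change.** - **SAP 4.3.1:** delete *correctly included* and restore the protocol's set: "randomized subjects that have at least one measurement on two of the periods Baha 6 Max SP, Baha 5 SP and unaided". If the term is kept, tie it to named entry criteria, judge them before database lock without sight of results, and report both primary results with and without any excluded subject.
- **SAP 4.3.2 and Protocol 9.5.2:** define per protocol as FAS subjects with no major protocol violation who have the analysed endpoint in the conditions being compared. For preference, that is a stated preference after both home periods. List what counts as a major violation.

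The cost is wording in two SAP sections. The change to Protocol 9.5.2 also needs a CIP amendment with Ethics Committee notification under Protocol 18. No subjects or data are added, and the planned 16 stays. The trade-off is that a subject later found ineligible remains in the FAS; the per-protocol analysis, with major violations defined, is the place to examine the effect of that.
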